## 9. DATA REPORTING

### 9.1 Definitions

**Adverse Event:** An Adverse Event (AE) is defined as any untoward medical occurrence in a patient or clinical investigation subject administered a pharmaceutical product and that does not necessarily have to have a causal relationship with this treatment. An AE can therefore be any unfavorable and unintended sign (including an abnormal laboratory finding), symptom, or disease temporally associated with the use of lenalidomide whether or not considered related to lenalidomide.

During clinical trials, adverse events can be spontaneously reported or elicited during open-ended questioning, examination, or evaluation of a subject. (In order to prevent reporting bias, subjects should not be questioned regarding the specific occurrence of one or more adverse events.)

AEs will be recorded in the case report form for the duration of the trial, regardless of whether or not the event(s) are considered related to trial medication. All AEs considered related to trial medication will be followed until resolution even if this occurs post-trial.

### **Serious adverse event (SAE)**

An adverse event occurring at any dose that results in any of the following outcomes (CFR 312.32):

- death
- a life-threatening adverse drug experience
- inpatient hospitalization or prolongation of existing hospitalization excluding those for study drug administration, transfusional support, disease staging/re-staging procedures, bone marrow biopsy or placement of an indwelling catheter, unless associated with other serious events.
- persistent or significant disability or incapacity,
- congenital anomaly / birth defect.

The definition of serious adverse event (experience) also includes *important medical event*. Medical and scientific judgment should be exercised in deciding whether expedited reporting is appropriate in other situations, such as important medical events that may not be immediately life-threatening or result in death or hospitalization but may jeopardize the patient or may require intervention to prevent one of the other outcomes listed in the definition above. These should also usually be considered serious. Examples of such events are intensive treatment in an emergency room or at home for allergic bronchospasm; blood dyscrasias or convulsions that do not result in hospitalization; or development of drug dependency or drug abuse. A new diagnosis of cancer during the course of treatment should be considered an important medical event.

The definition of “related” being that there is a reasonable possibility that the drug caused the adverse experience.

### **Unexpected Adverse Event**

An adverse event that is not mentioned in the Investigator's Brochure or package insert or the specificity or severity of which is not consistent with the investigator's brochure or package insert.

### **Life-threatening**

Any adverse drug experience that places the patient or subject, in the view of the investigator, at immediate risk of death from the reaction as it occurred. It does not include a reaction that, had it occurred in a more severe form, might have caused death.

Adverse events (AEs) will use the descriptions and grading scales found in the revised

Common Terminology Criteria for Adverse Events (CTCAE) version 4.0.

## 9.2 Determination of reporting requirements

Steps to determine if an adverse event is to be reported in an expedited manner:

**Step 1:** *Identify the type of event using the NCI Common Terminology Criteria for Adverse Events (CTCAE) Version 4.0.* The CTCAE provides descriptive terminology and a grading scale for each adverse event listed. A copy of the CTCAE can be downloaded from the CTEP home page (<http://ctep.cancer.gov>). Additionally, if assistance is needed, the NCI has an Index to the CTCAE that provides help for classifying and locating terms. All appropriate treatment locations should have access to a copy of the CTCAE.

**Step 2:** *Grade the event using the NCI CTCAE.*

**Step 3:** Determine whether the adverse event is related to the protocol therapy (*lenalidomide*). Attribution categories are as follows: Unrelated, Unlikely, Possible, Probable, and Definite.

**Step 4:** Determine the prior experience of the adverse event. Expected events are those that have been previously identified as resulting from administration of the agent. An adverse event is considered unexpected, for expedited reporting purposes only, when either the type of event is **NOT** listed in section 2.5 or in drug-insert.

**Step 5:** Review the "Additional instructions, requirements, and exceptions for this protocol specific requirements for expedited reporting of specific adverse events that require special monitoring.

**Step 6:** Determine if the protocol treatment given prior to the adverse event included investigational agent(s), a commercial agent(s), or a combination of investigational and commercial agents.

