**Adverse Events**

Most frequently reported adverse events reported during clinical studies with lenalidomide in oncologic and non-oncologic indications, regardless of presumed relationship to study medication include: anemia, neutropenia, thrombocytopenia and pancytopenia, abdominal pain, nausea, vomiting and diarrhea, dehydration, rash,

itching, infections, sepsis, pneumonia, Urinary Tract Infections (UTI) , Upper respiratory infection, atrial fibrillation, congestive heart failure, myocardial infarction, chest pain, weakness, hypotension, hypercalcemia, hyperglycemia, back pain, bone pain, generalized pain, dizziness, mental status changes, syncope, renal failure, dyspnea, pleural effusion, pulmonary embolism, deep vein thrombosis, Cerebrovascular attacks (CVA), convulsions, dizziness, spinal cord compression, syncope, disease progression, death not specified and fractures.

Lenalidomide has been studied in healthy volunteers and in patients with cancer of the blood and other organs of the body as well as in patients with other diseases. As with any other experimental treatment there may be side effects or risks associated with lenalidomide, some of which are not yet known.

The following is a list of the most medically significant or most common side effects reported in completed and ongoing studies considered to be related to lenalidomide. In some cases, side effects can be serious, long-lasting, may never go away, or can cause death.

Common (between a 1-10% chance that this will happen):

Anemia; Decrease in cells that help your blood clot; Low white blood cells with or without fever; Pneumonia or other infections; Fever; Abnormal heart beats; Shortness of breath; Blood clots in lower extremities, lungs, heart, brain or other organs; Abnormal kidney function; Diarrhea with or without bleeding; Loss of fluid; Other cancers; Pain including muscles, joints and non-heart pain; Altered sense of taste.

Uncommon (between a 0.1-1% chance that this will happen):

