### 9.5 Expedited reporting

This section outlines adverse events that require expedited reporting.

The following be reported as a SAE:

- **Grade 2 (moderate) and Grade 3 (severe) Events** – Only events that are Unexpected and Possibly, Probably or Definitely Related/Associated with lenalidomide.
- **ALL Grade 4 (life threatening or disabling) Events** – Unless expected AND specifically listed in protocol as not requiring reporting (see section 9.8).
- **ALL Grade 5 (fatal) Events** – When participant is enrolled and actively participating in the trial OR when event occurs within 30 days of the last study intervention.

MEDWATCH 3500A form will be used to report SAEs to Montefiore Medical Coordinating Center and to Celgene Corporation for this study.

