### **9.10 Responsibilities of the Coordinating Center (Montefiore Medical Center) and Celgene Corporation.**

The Coordinating Center (Montefiore Medical Center) will maintain records and provide reports to Celgene Corporation for the following Adverse Experiences:

1. All serious, unexpected, adverse events,
2. Any significant increase in the frequency of serious expected adverse events, and
3. An annual progress report including number of patients accrued, date on study, date off study, vital status (alive/dead and date alive/dead).

Celgene Corporation will supply study drug, lenalidomide free of charge.

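### Section 9 has two conflicting definitions of an unexpected event; the one used for expedited reporting ignores severity and specificity, which affects related, non-serious Grade 2–3 events

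*Combined protocol and SAP*

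**What the plan says.** Section 9.1 gives a general definition with two limbs. An event is unexpected if the investigator's brochure or package insert does not mention it, or if it is one "the specificity or severity of which is not consistent with the" brochure or insert.

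Section 9.2, Step 4, gives a second definition for routing reports. It first says "Expected events are those that have been previously identified as resulting from administration of the agent". It then continues: "An adverse event is considered unexpected, for expedited reporting purposes only, when either the type of event is" not found in Section 2.5 or the drug insert. Neither sentence mentions severity or specificity.

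The first adverse-event list in Section 2.5 is introduced as "Most frequently reported adverse events reported during clinical studies with lenalidomide in oncologic and non-oncologic indications, regardless of presumed relationship to study medication include", and it closes with "disease progression, death not specified and fractures".

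The word is then used in two places. In Section 9.5, Grade 2 and Grade 3 events are reported as SAEs under this restriction: "Only events that are Unexpected and Possibly, Probably or Definitely Related/Associated with lenalidomide". In Section 9.10, the coordinating centre's reports to the supplier cover "All serious, unexpected, adverse events", without saying which definition is meant.

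**The concern.** Two sites could each follow Section 9 faithfully and classify the same event differently. Under 9.1, a listed type of event that appears in a worse or more specific form than the reference describes is unexpected. Under Step 4 the form is irrelevant once the type is listed. A broad term such as infections would cover an unusual infection that the specificity limb of 9.1 is there to catch.

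The reference sources also differ. Section 9.1 uses the brochure or insert; Step 4 uses Section 2.5 or the insert. Step 4 also sits badly with itself: it describes expected events as those already attributed to the drug, then points to a section whose first list was compiled without regard to attribution.

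Safety is part of the primary objective (Section 1.1). Dose-limiting toxicity is assessed in the first cycle of Phase 1, while treatment can continue indefinitely (Section 5.4) and 30 patients enter Phase 2 (Section 5). After cycle 1, prompt notice of toxicity beyond the known profile depends on the reporting rules.

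**Working it through.** The plan gives no figure to reproduce here. The check sets the definitions side by side and follows an event through the rules.

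**Step 1: the two tests.**

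| | Section 9.1 | Section 9.2, Step 4 |
|---|---|---|
| Scope | General | Expedited reporting only |
| Type not listed | Unexpected | Unexpected |
| Type listed, severity or specificity beyond the reference | Unexpected | Not addressed |
| Reference | Brochure or insert | Section 2.5 or insert |

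**Step 2: what the either/or in Step 4 can mean.** Let A be the types listed in Section 2.5 and B those in the insert. If an event must be absent from both sources, it is unexpected when it lies outside A ∪ B. If absence from one is enough, it is unexpected when it lies outside A ∩ B. The readings differ for types found in only one source. For a type in both, the event is not unexpected on either reading, whatever its severity. The insert is only linked (Appendix G), so A ∩ B cannot be counted.

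**Step 3: breadth of Section 2.5.** The first list has 43 entries. Dizziness and syncope each appear twice, so 43 − 2 = 41 are distinct. The later lists, of events considered related to the drug, have 14 common, 34 uncommon and 51 rare entries, with overlap between lists. None carries CTCAE grades. These counts describe the list; they do not estimate how many events would be reclassified.

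**Step 4: routing.** Take an event related to lenalidomide, of a type listed in both sources, with severity or specificity beyond the reference. Apply Sections 9.5, 9.8 and 9.9.

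| Event | Under 9.1 | Under Step 4 | Does the definition matter? |
|---|---|---|---|
| Grade 2, not hospitalised, not otherwise serious | Expedited | Routine | Yes |
| Grade 3, same, outside Table 5 | Expedited | Routine | Yes |
| Grade 2, hospitalised | Expedited | Outside the grade trigger and the Grade 3–5 hospitalisation rule, but an SAE under 9.1, so copied to the coordinating centre within two working days (9.9) | Route and timing at most |
| Grade 3, hospitalised, outside Table 5 | Expedited | Expedited | No |
| Grade 4, outside Table 5 | Expedited | Expedited | No |
| Grade 5, on study or within 30 days | Expedited | Expedited | No |
| Disability or congenital anomaly | Expedited | Expedited | No |
| Grade 3–4 anemia, neutropenia or thrombocytopenia attributed to the drug | Table 5 rule | Table 5 rule | Taken as no, since Table 5 names the grades |

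**Step 5: size of the difference in timing.** Section 9.5 gives expedited timelines of 24 hours plus a full report within 5 calendar days, or 10 calendar days. It does not say which applies to Grade 2–3 events. Routine reporting is by adverse event log (9.3), with data submitted every 4 weeks (Section 11).

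**The case against.** The strongest reply is that most escalation routes never ask whether an event was expected. The table above bears this out. In addition, second primary malignancies are SAEs regardless of cause (9.6), and the SAE definition in 9.1 includes important medical events. That stands, and it sets the limit of this point.

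A reader might infer more: that related toxicity worse than known goes unescalated in general, or that a related death or Grade 4 event of a listed type is lost to the supplier through 9.10. The documents do not support either inference. Sections 9.5 and 9.9 have SAEs sent to the coordinating centre and directly to the supplier, with no expectedness filter at that step. Step 4 limits itself to expedited reporting, so the 9.1 definition is the more natural one for 9.10. The same section also covers a significant increase in serious expected events. For 9.10, what remains is that the governing definition is not named.

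It can also be said that the opening sentence of Step 4 weighs against letting a causality-blind list make an event expected. That is a fair reading, but the next sentence points to Section 2.5 without separating its lists, so the site is left to choose. A reader might take the word either as a sign that a second limb on severity was lost. It pairs grammatically with the two named sources, so that is conjecture.

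Finally, the effect is on timing. All adverse events are recorded whatever their relationship (9.1), DLTs do not depend on expectedness (5.1), and there are biweekly calls and monthly committee review (11.1). This also stands: neither the safety data set nor the dose-escalation decisions are altered.

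**Conclusion.** The conflict is real and can be read directly from Sections 9.1 and 9.2. Its practical effect is narrow: related, non-hospitalised, otherwise non-serious Grade 2–3 events of a listed type whose severity or specificity goes beyond the reference. These are expedited under one definition and routine under the other. A secondary uncertainty is whether a type listed in only one of the two Step 4 sources is expected.

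The number of events affected cannot be derived from the documents. They do not reproduce the insert or brochure, give no expected rate of such events, and so do not allow known severities to be checked. The conclusion assumes that Step 4 is applied as written to the Grade 2–3 trigger and that Table 5 governs the three cytopenias by itself. It is worth correcting because the rule as written slows notice of the events that the severity and specificity limb is meant to bring forward, and the correction is small.

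**What to change.** Replace the Step 4 test with the 9.1 definition: an event is unexpected if its type is not listed in the reference, or if its specificity or severity is not consistent with it. Name the same reference document in 9.1 and in Step 4, which also removes the either/or ambiguity. State that the first list in Section 2.5, compiled regardless of relationship to the drug, does not make an event expected. Add a few words to 9.10 saying that the same definition applies there.

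This is essentially a one-sentence amendment with matching cross-references. It changes no dose, sample size or analysis. The cost is somewhat more expedited Grade 2–3 reports for the sites and the coordinating centre.

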## 9.3 Reporting methods

Adverse event log form (using Montefiore-Einstein AE form) should be faxed or emailed to the Montefiore Medical Coordinating Center.

## 9.4 When to report an event in an expedited manner

This trial will be monitored by the Albert Einstein Cancer Center Data Safety Monitoring Committee (AECC DSMC). Data monitoring plan is provided in Section 11.1.

Follow guidelines in section 9.5 regarding criteria that required reporting of adverse events that required require 24-hour notification.

For any adverse events that occur more than 30 days after the last dose of treatment, only those that have an attribution of possibly, probably, or definitely must be reported on an expedited adverse event report form.

### 9.5 Expedited reporting

This section outlines adverse events that require expedited reporting.

The following be reported as a SAE:

- **Grade 2 (moderate) and Grade 3 (severe) Events** – Only events that are Unexpected and Possibly, Probably or Definitely Related/Associated with lenalidomide.
- **ALL Grade 4 (life threatening or disabling) Events** – Unless expected AND specifically listed in protocol as not requiring reporting (see section 9.8).
- **ALL Grade 5 (fatal) Events** – When participant is enrolled and actively participating in the trial OR when event occurs within 30 days of the last study intervention.

MEDWATCH 3500A form will be used to report SAEs to Montefiore Medical Coordinating Center and to Celgene Corporation for this study.

#### Expedited AE reporting timelines:

**24 Hours; 5 calendar days** – The investigator must initially report the AE within 24 hours of learning of the event followed by a completed AE report within 5 calendar days of the initial 24-hour report.

**10 calendar days** – A complete AE report on the AE must be submitted within ten calendar days of the investigator learning of the event. Any medical event equivalent to CTCAE grade 3, 4, or 5 that precipitates **hospitalization (or prolongation of existing hospitalization)** must be reported regardless of attribution and designation as expected or unexpected with the exception of any events identified as protocol specific expedited adverse event reporting exclusions (Section 9.8)

Hospitalizations are defined as lasting 24 hours or longer and these events must be reported via an expedited manner.

Any event that results in persistent or significant disability/incapacity, congenital anomaly, or birth defect must be reported via an expedited AE mechanism.

**Additional instructions, requirements and exceptions for this protocol:**

With respect to determining the specific day by which the event must be reported, the day the reporter learns of the adverse event constitutes “Day 0”.

**9.6 Reporting Second Primary Malignancies (SPMs)**

SPMs are considered events of interest and should be included as part of the assessment of adverse events throughout the course of the study. Investigators are to report any second primary malignancies as serious adverse events regardless of causal relationship to lenalidomide, occurring at any time for the duration of the study. For all subjects who develop second primary malignancies, sites will be required to submit all diagnostic reports (e.g. pathology, cytogenetics, flow cytometry results) from the indication diagnostic confirmation samples submitted at screening and all reports for the tumor samples from the SPM diagnosis. For SPMs diagnosed at another institution (outside the investigational site) sites are to make every effort to obtain these reports for the SPM confirmation.

**9.7 Reporting Pregnancies**

Pregnancies and suspected pregnancies (including a positive pregnancy test regardless of age or disease state) of a female subject occurring while the subject is on lenalidomide, or within 30 days of the subject’s last dose of lenalidomide, are considered immediately reportable events. Lenalidomide is to be discontinued immediately. The pregnancy, suspected pregnancy, or positive pregnancy test must be reported to Montefiore Medical Center Coordinating Center AND Celgene Drug Safety immediately by facsimile, or other appropriate method, using the Pregnancy Initial Report Form, or approved equivalent form. Local IRB should be notified per institutional guidelines. The female subject should be referred to an obstetrician-gynecologist, preferably one experienced in reproductive toxicity for further evaluation and counseling.

The Investigator will follow the female subject until completion of the pregnancy, and must notify Montefiore Medical Center Coordinating Center AND Celgene Drug Safety immediately about the outcome of the pregnancy (either normal or abnormal outcome) using the Pregnancy Follow-up Report Form, or approved equivalent form. If the outcome of the pregnancy was abnormal (e.g., spontaneous or therapeutic abortion), the Investigator should report the abnormal outcome as an AE. If the abnormal outcome meets any of the serious criteria, it must be reported as an SAE to Montefiore Medical Center Coordinating Center AND Celgene Drug Safety immediately by facsimile, or other

appropriate method, within 24 hours of the Investigator’s knowledge of the event using MEDWATCH 3500A form.

All neonatal deaths that occur within 30 days of birth should be reported, without regard to causality, as SAEs. In addition, any infant death after 30 days that the Investigator suspects is related to the in utero exposure to lenalidomide should also be reported to Montefiore Medical Center Coordinating Center AND Celgene Drug Safety immediately by facsimile, or other appropriate method, within 24 hours of the Investigator’s knowledge of the event using MEDWATCH 3500A form.

**9.8 Protocol-Specific Expedited Adverse Event Reporting Exclusions**

For this protocol only, certain AEs/grades are exceptions to the Expedited Reporting Guidelines and do not require reporting in an expedited manner. The following AEs (Table 5) must be reported through the routine reporting mechanism (Section 9.1):

**Table 5:**Expedited Adverse Event Reporting Exclusions

CTCAE Category	Adverse Event	Grade	Hospitalization / Prolongation of Hospitalization	Attribution	Comments
Blood and lymphatic system	Anemia	3-4	n/a	Lenalidomide	lenalidomide produces expected myelosuppression.
Blood and lymphatic system	Neutropenia	3-4	n/a	Lenalidomide	As above; report only if longer than 15 days unless related to relapsed AML
Blood and lymphatic system	Thrombocytopenia	3-4	n/a	Lenalidomide	As above; report only if longer than 15 days unless related to relapsed AML

**9.9 Responsibilities of Participating Sites**

Adverse events will be reported to each participating institution according to protocolguidelines and local policies and procedures governing the local Institutional Review Board.

A principal Investigator in a participating institution is required to notify Institutional Review Board (IRB) of a serious adverse event according to institutional policy.

A copy of all SAE's as defined in section 9.1 should be faxed to the Coordinating Center, Montefiore Medical Center within two working days by the participating site. All Events described in protocol sections 9.6 and 9.7 must be reported via an expedited AE mechanism.

Participating study sites should NOT report SAEs to the FDA. Rather, participating sites should report SAEs to the primary study site, Montefiore Medical Center and to Celgene. The primary site will be responsible for reporting to FDA.

